4.3.10.3 INITIATING THE GLUCOSE CHALLENGE

Hyperglycemia challenges may be initiated by administering a mixed meal of (30 to 40%) carbohydrate content gradually targeting maintaining a glucose level of >300 mg/dL for 75 minutes, based on subject's insulin/carbohydrate ratio. Liquid carbohydrates (such as Boost, soda, juice) can be given in small volumes only if the mixed meal is not successful in reaching the target. Hypoglycemia challenges may be initiated by administrating SQ fast-acting insulin targeting maintaining <70 mg/dL for 1 hour, based on subject's insulin sensitivity ratio. Details about all carbohydrates (time, type and amount) will be recorded for entry into the study database, as well as all bolus insulin given.

4.3.11 DOWNLOADING DEVICES

The study issued Subject SMBG meter and the Transmitter(s) will be downloaded at the end of each sensor accuracy visit (Days 1-180 visits), during each clinic visit for subjects in the cohort continuing to 365 days, or at any unscheduled visit as appropriate. Transmitter data will also be uploaded to a data management system to monitor calibration compliance. Additionally, for the subjects continuing to 365 days of sensor wear with the secondary sensor and a new primary sensor, accuracy of the new 180 day primary sensor will be monitored for performance approximately every 2 weeks. Since the compliance monitoring of the daily SMBG entry will continue on for the second primary sensor, the performance monitoring with use entered SMBG points to assess that the accuracy is within the distribution of the 20/20% agreement per day from the PRECISE II study throughout that two week monitoring interval. If performance is not restored to within the PRECISE II distribution within 2 weeks, the 180-day sensor will be placed in blinded

Clinical Mode for the remainder of the study. The subject will be blinded to glucose values, alerts and alarms.

4.3.12 HbA1c BLOOD DRAW

Blood samples will be drawn for HbA1c measurement at the 90-day, 180-day, and 365-day visits, as applicable. All samples will be collected and processed as described in the instructions provided by the central lab.

4.3.13 QUESTIONNAIRES

At visits 8 (Day 90 visit), 11 (Day 180 visit), and 15 (Day 365 visit) subjects will complete the Diabetes Distress Scale questionnaire. At the removal visit, subjects will complete the CGM Satisfaction questionnaire. Subjects who have a sensor enter Clinical Mode prior to the designated visits, the Diabetes Distress Scale questionnaire and CGM Satisfaction questionnaire may be completed at the visit following confirmation of Clinical mode.

4.3.14 DISCHARGE INSTRUCTIONS – SENSOR ACCURACY VISITS

The discharge procedure will occur upon completion of visit related activities. Blood glucose (either SMBG or YSI) and ketone measurements will be assessed. If the glucose level is <75 mg/dL or >300 mg/dL, corrective action will be taken by the investigator. Subjects may be discharged when they have had 2 glucose readings taken at least 15 minutes apart that are >75 and < 300 mg/dL. Ketones should be ≤ 1.5 mmol/L. Site will document any adverse events that may have occurred during the visit.

Additional inpatient time for BG stabilization will not be considered an adverse event or protocol deviation.

Subjects will be provided a standard meal or snack as necessary prior to release to prevent post-discharge hypoglycemia. Snacks will be available in the clinic for subjects to take with them on the ride home.

A clinician trained in the treatment of diabetes should also discuss and make recommendations about each subject's insulin regimen for the remainder of the day to prevent post-visit rebound hypoglycemia which can occur 12 hours later.

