4.3.5 KETONE TESTING

Ketone (β -hydroxybutyrate (β -HOB)) measurements will be made using a study supplied FDA-approved self-monitoring ketone meter and strips as described in 5.2.3. Subject blood ketones should be evaluated from capillary or venous blood using the ketone meter while in the clinic for sensor insertion and accuracy visits at the following times:

- On arrival and at discharge from the clinic
- Glucose ≥ 300 mg/dL (measure approximately within 20 minutes of the first glucose reading > 300 mg/dL and repeat approximately every 60 minutes until < 300 mg/dL)
- Ketones ≥ 0.6 mmol/L (repeat approximately every 60 minutes until < 0.6 mmol/L)
- Subject has nausea, vomiting or abdominal pain regardless of glucose level.

Treatment guidelines for ketones can be found in section 7.5.3.

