7.5.2 HYPERGLYCEMIA AND BLOOD KETONE MONITORING

The Subject will be asked to alert the study team anytime he or she notes symptoms of hyperglycemia (i.e. thirst, increased urination, or other symptoms). A glucose level will be confirmed by YSI or Subject SMBG meter.

Fingerstick blood ketones, using a commercially available ketone meter, will be monitored if blood glucose ≥ 300 mg/dL hourly until resolved. If glucose >400 mg/dL and no symptoms and no ketones, the cause of the hyperglycemia will be investigated and treated as appropriate by the Investigator.

If blood ketones > 1.5 mmol/L; subject participation in glucose challenges will be stopped for the day (see below). Appropriate care will be provided, including fluids and insulin as determined by Investigator. Standard-of-care troubleshooting for insulin pump users will take place, including change of infusion set if indicated and insulin by injection if indicated. If the subject's home parameters are not felt to be working adequately due to hyperglycemia, ketonemia, or other factors (e.g. intercurrent illness), the study MD

or NP will administer corrective insulin either via insulin syringe or via a new pump site using an ISF determined to be appropriate for the setting and a goal glucose of 120 mg/dL. The subject will continue to be monitored until a glucose level between 100-300 mg/dL and ketone measurement <0.6 mmol/L has been achieved (or the subject is discharged to an appropriate medical team).

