7.5.3 GUIDELINES FOR TREATMENT OF HYPERGLYCEMIA AND KETONES WHEN NOT IN A CHALLENGE

Subject safety prevails, and Investigator may treat for hyperglycemia when clinically indicated at any time. However, when the subject is not in a challenge and becomes hyperglycemic and safety is a concern, the guidelines below should be followed to treat the hyperglycemia.

Ketone				
BG		<0.6	0.6-1.5	>1.5
	<300	
 Ketone testing will be repeated hourly until <0.6 Subject will be treated with SQ or IV insulin targeting 120mg/dL using subject's insulin sensitivity factor 	
 Glucose challenges will be stopped, and subject will enter free range glucose control Ketone testing will be repeated hourly until <0.6 Subject will be treated with SQ or IV insulin targeting 120mg/dL using subject's insulin sensitivity factor 	
>300		
 Ketone testing will be repeated hourly until BG <300 	
 Ketone testing will be repeated hourly until <0.6 Subject will be treated with SQ or IV insulin targeting 120mg/dL using subject's insulin sensitivity factor Continue monitoring until BG <300 	
 Glucose challenges will be stopped, and subject will enter free range glucose control Ketone testing will be repeated hourly until <0.6 Subject will be treated with SQ or IV insulin targeting 120mg/dL using subject's insulin sensitivity factor Continue monitoring until BG <300

- Insulin treatment for hyperglycemia or ketones should be done using the subject's own insulin. In the event that the subject's own insulin appears to be compromised (not having the expected effect on the subject's blood glucose), appropriate insulin (based on the subject's normal insulin type and concentration) provided by the site may be used.

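### The accuracy-visit discharge limit for ketones (1.5 mmol/L) is not reconciled with testing and monitoring obligations elsewhere in the protocol that run until below 0.6 mmol/L

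*Protocol*

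**What the plan says.** **Discharge (Protocol 4.3.14).** Ketones and glucose are assessed before release from an accuracy visit. The ketone condition is "Ketones should be ≤ 1.5 mmol/L". The glucose condition is "2 glucose readings taken at least 15 minutes apart that are >75 and < 300 mg/dL". The section does not refer to any other ketone rule.

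**Ketone testing (Protocol 4.3.5).** Ketones are measured "while in the clinic for sensor insertion and accuracy visits at the following times". One of those times is "On arrival and at discharge from the clinic". Another is "Ketones ≥ 0.6 mmol/L (repeat approximately every 60 minutes until < 0.6 mmol/L".

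**Monitoring (Protocol 7.5.2).** One paragraph is triggered by ketones above 1.5 mmol/L. It stops challenges for the day, describes care and corrective insulin, and ends: "The subject will continue to be monitored until a glucose level between 100-300 mg/dL and ketone measurement <0.6 mmol/L has been achieved". The only exception is discharge to an appropriate medical team.

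**Treatment guideline (Protocol 7.5.3).** The table contains cells reading "Ketone testing will be repeated hourly until <0.6". The guideline applies outside a challenge, when the subject becomes hyperglycemic and safety is a concern.

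**Meters (Protocol 5.2.3).** Ketone meters stay at the clinical site and are not given to subjects.

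**SAP 4.3.** The SAP repeats the hourly ketone assay from 0.6 mmol/L at the Day 1 to Day 180 visits. It says nothing about release.

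**The concern.** A site working from 4.3.14 can send a subject home whom 4.3.5 still requires to be retested, or whom 7.5.2 still requires to be monitored. The study raises glucose on purpose: 4.3.10.3 targets more than 300 mg/dL for 75 minutes. Recovery and discharge preparation follow the challenge window in the visit tables, so the discharge decision comes when this matters.

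Two things are at stake. One is subject safety, if practice falls to the looser reading by default. The other is consistency: with up to 15 sites, staff can reasonably follow different sections, and a release that complies with 4.3.14 could be recorded as a deviation from 4.3.5 or 7.5.2. Sections 4.3.14 and 4.3.16 allow extra clinic time for glucose stabilization, but neither mentions extra time for ketones.

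**Working it through.** There is no stated figure to reproduce. The check compares thresholds.

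**Step 1. Ketone overlap.** 4.3.14 permits release at 1.5 mmol/L or below. 4.3.5 keeps repeats running at 0.6 mmol/L or above. Both hold from 0.6 to 1.5 mmol/L inclusive, a band of 1.5 − 0.6 = 0.9 mmol/L.

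| Ketones at end of visit (mmol/L) | Exceeded 1.5 during the visit? | 4.3.14 ketone limit | 4.3.5 repeat | 7.5.2 end of monitoring |
|---|---|---|---|---|
| Below 0.6 | No | Met | None due | Not engaged |
| Below 0.6 | Yes | Met | None due | Ketone part met; glucose must also be 100-300 mg/dL |
| 0.6-1.5 | No | Met | Still due | Not engaged |
| 0.6-1.5 | Yes | Met | Still due | Not met |
| Above 1.5 | Yes | Not met | Still due | Not met |

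Rows 3 and 4 are the ketone conflict. Below 0.6 and above 1.5 the ketone thresholds agree.

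**Step 2. Glucose overlap.** 4.3.14 accepts readings above 75 mg/dL and 7.5.2 starts at 100 mg/dL. In whole numbers the gap is 76-99 mg/dL. It matters only in the rows where ketones exceeded 1.5, because only then is 7.5.2 engaged.

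**Step 3. Worked cases.**
- Ketones 1.2 mmol/L at discharge, never above 1.5, two glucose readings of 200 mg/dL. 4.3.14 is met. The discharge test that 4.3.5 itself requires triggers that section's hourly repeat.
- Ketones rise above 1.5, are treated and fall to 1.0 mmol/L, with glucose 200 mg/dL. 4.3.14 is met; 7.5.2 is not.
- Ketones rise above 1.5 and fall below 0.6, with glucose 85 mg/dL. 4.3.14 is met and no repeat is due under 4.3.5, but the glucose part of 7.5.2 is not met.

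**Step 4. Can the repeats be finished after release?** Not with the study meter, which stays at the site under 5.2.3.

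**Step 5. What 7.5.3 adds.** Its 0.6-1.5 column reads clearly in the row for glucose above 300 mg/dL, but 4.3.14 already bars discharge there. The relevant row is glucose below 300. In the text as extracted from the PDF, that row has two filled cells for three ketone columns, so placing the first under 0.6-1.5 is by analogy with the other row. It is supporting evidence only.

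**Step 6. Exposure.** Each subject has one Visit 3 and one Visit 4, then Visits 5 to 11: 2 + 7 = 9 accuracy visits. The documents give no rate of ketones in the 0.6-1.5 band.

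**The case against.** **The rules can be followed together.** 4.3.14 places discharge after the visit's activities are complete, and its wording is permissive. If hourly repeats count as visit activities, they come first and 1.5 mmol/L is only an outer limit. A site that holds a subject until below 0.6 breaches nothing. This stands in part: no rule forbids what another requires, so the problem is unresolved precedence and not a strict logical contradiction. But the protocol never says that repeats must finish first, and that reading would leave the 1.5 limit with little function.

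**4.3.5 and 7.5.3 are testing rules.** This stands. Neither is written as a release criterion, and 4.3.5 applies in the clinic, so it could be read as lapsing when the subject leaves. Against that, 4.3.5 requires a test at discharge and runs until a value is reached, and the meter does not go home.

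**7.5.2 covers a narrower group.** This also stands. A stricter rule for subjects who exceeded 1.5 mmol/L can sit beside a general one, and there is a hand-over exception. Its monitoring sentence follows one on corrective insulin, so it might cover only subjects so treated. Even then, 4.3.14 does not exempt that group from its own limits or point to 7.5.2.

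**Safeguards exist.** The investigator has ultimate responsibility (7.1), sites have their own safety guidelines (7.2), subjects have a 24-hour contact (4.2.5), and a clinician advises on insulin for the rest of the day (4.3.14). These reduce the likely harm but do not say which rule governs release.

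**A stronger reading.** A reader might infer that three other sections set rival release criteria for every subject, and that two glucose ranges compete at every discharge. The documents do not support this. Two of the three are continuing-test rules, 7.5.3 is a conditional guideline, and the 100-300 mg/dL range belongs to the paragraph on ketones above 1.5.

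**Conclusion.** The concern holds as an unresolved conflict between the discharge limit in 4.3.14 and continuing obligations in 4.3.5 and 7.5.2. It applies to ketones of 0.6-1.5 mmol/L at the end of an accuracy visit and, only where ketones exceeded 1.5 mmol/L, to glucose of 76-99 mg/dL. The 4.3.14 against 7.5.2 conflict is the more direct, because 7.5.2 sets an explicit end to monitoring; the 4.3.5 conflict reaches more subjects, because it starts at 0.6 mmol/L.

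This rests on two assumptions: that a repeat due under 4.3.5 does not simply lapse at release, and that the last sentence of the 7.5.2 paragraph applies to subjects whose ketones exceeded 1.5 mmol/L. It does not depend on 7.5.3. The consequence is for safety and uniform conduct, at an unknown frequency. It has no bearing on MARD or the sample size. It should be corrected, and it takes no position on which threshold is right.

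**What to change.** Reconcile 4.3.5, 4.3.14, 7.5.2 and 7.5.3, with cross-references in 4.3.14. The text should state:
- which ketone condition governs release, and whether a repeat due under 4.3.5 or 7.5.3 must be completed first or ends at discharge;
- whether subjects whose ketones exceeded 1.5 mmol/L are released under 4.3.14 or 7.5.2, including which glucose range applies to them;
- to whom the monitoring sentence in 7.5.2 applies.

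The clinical team should choose the thresholds. The cost is a few sentences in a protocol clarification, the approvals that 13.4 requires, and a training update for sites. No analysis changes. The ketone line in SAP 4.3 needs editing only if the 4.3.5 testing rule itself is altered.

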4.3.15 ESTIMATED TOTAL BLOOD VOLUME

Approximately 43-51 blood samples will be obtained throughout the course of each of the respective visits in addition to the blood samples (2 ml) required for HbA1c analysis (as required) and fingersticks. The estimated amount of blood for each accuracy visit is approximately 2 ml per sample, exclusive of lab draws.

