4.1 VISIT 1 - SCREENING/ENROLLMENT

Subjects will be enrolled into the study following informed consent. Screening evaluation will determine subject eligibility for sensor insertion. No study-specific procedures may be performed prior to informed consent signature. The Screening Visit is anticipated to last approximately 2 hours. The visit will occur within 45 days before the Sensor Insertion Visit (V2). In the event that an insertion visit cannot be scheduled within the 45 day window, a qualified subject may repeat the screening visit.

The Screening Visit includes performing/collecting the following information:

- Demographics - including age, gender at birth, race/ethnicity, dominant hand, and BMI
- Diabetes History - including type of diabetes, date of diagnosis or length of diabetes, history of DKA and severe hypoglycemia, current treatment (type of insulin and type of insulin delivery (injections or insulin pump), insulin doses, and when applicable: basal rates, correction factors, glucose targets, insulin duration, insulin to carbohydrate ratios).
- Current and Past Medical History - including concomitant medications
- Physical examination and vital signs - including height, weight, blood pressure, pulse, temperature, assessment of potential sensor insertion sites, assessment of venous access for repeated blood draws
- EKG - An EKG will be performed with the results kept in the subject records
- Laboratory - Blood samples (approximately 2 ml total) will be drawn for hemoglobin A1c (HbA1c)
- Quality of Life questionnaire - The diabetes distress scale will be administered

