4.3.9.2 TIMING OF BLOOD SAMPLING

Blood will be sampled approximately every 5 to 15 minutes, dependent on the value of the previous sample according to the following ranges:

- BG \geq 300 mg/dL: every 5 minutes (+/- 2 minutes) *
- BG >70 mg/dL and < 300 mg/dL: every 15 minutes (+/- 2 minutes)
- BG \leq 70 mg/dL: every 5 minutes (+/- 2 minutes)

*When > 400 mg/dL, sampling may be reduced to every 15 minutes

Blood sampling can also be reduced to every 15 minutes after the challenge is met. Additional samples may be drawn for YSI glucose analysis as needed for patient safety or to recheck a suspected erroneous value (e.g. dilute sample).

In the event of loss of IV access or loss of functional YSI and need for continued subject monitoring, glucose measurements will be made on capillary whole blood using the Subject SMBG meter as needed.

Samples missed due to loss of IV access or other interruptions will not be considered protocol deviations.

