4.3.9.3 SAMPLE VOLUME

Approximately 0.5 ml IV blood samples will be collected (after 1.5 ml waste is cleared from sampling apparatus) in sample containers with an appropriate anticoagulant additive (BD Microtainer K2E tubes (REF 365955) or Sarstedt Monovette with K2E (REF 06.1664.001) or similar) for analysis.

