6 CLINICAL LABORATORY EVALUATIONS AND ESTIMATED BLOOD VOLUMES

Standard clinical laboratory analysis equipment, procedures and quality control will be used for all laboratory evaluations in this clinical trial. Blood samples will be drawn for glycemic challenges and for laboratory measurement of HbA1c. Blood loss will not exceed the American Red Cross Guidelines of more than 475 ml over any 8-week period. Hematocrit will be assessed using local lab or Point of Care testing device.

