8.5 RISKS ASSOCIATED WITH PARTICIPATION IN THE CLINICAL INVESTIGATION

This clinical investigation involves subjects with diabetes mellitus. These subjects may experience hyperglycemia and hypoglycemia as a consequence of their existing condition and medical management (e.g. insulin administration). For this study, hyperglycemia and hypoglycemia will not be reported as adverse events unless meeting criteria of a Serious Adverse Event. Episodes of hyperglycemia and hypoglycemia as documented by the Subject SMBG Meter will be reported in an extra listing separate from the AE listings. Should a known side effect(s) occur to administered medication(s) used in the intervention, such effects will be reported as part of the adverse event description and will not be considered a separate adverse event.

The amount of blood drawn for in-clinic testing during the study is below the acceptable limits of blood donation of approximately 475 mL per 8 weeks; hence it does not pose any additional unacceptable risk to the subjects.

This clinical investigation involves the following procedures that present risk: placement of an intravenous catheter, frequent blood sampling, and conduct of hyperglycemia and hypoglycemia challenges at the clinic visits. In addition, Subjects in this study may use an insulin pump or syringes to administer subcutaneous insulin.

The following risks are potentially associated with such procedures:

- Routine administration of insulin may cause hematoma, redness, swelling and itch at the injection site, skin rash, itch, sweating, gastro-intestinal complaints, edema, difficulty breathing, palpitations and drop in blood pressure, and even death.
- Hypoglycemic symptoms requiring medical intervention which may include seizures, neuroglycopenia, coma and even death (including occurrence during home use)
- Insulin administration leading to hypoglycemia include: cold sweating, cool and pale skin, fatigue, nervousness, shakiness, anxiety, weakness, confusion, feeling of numbness, hunger, impairment of vision, problems with concentration, headache, nausea, palpitations, coma, or death.

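### The 475 mL per 8-week blood-loss limit holds on planned figures but is not guaranteed: five accuracy visits can fall within 56 days, leaving a 43-55 mL margin and no cumulative check

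*Protocol*

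**What the plan says.** Protocol section 6 states the limit without condition: "Blood loss will not exceed the American Red Cross Guidelines of more than 475 ml over any 8-week period". Section 8.5 says that the amount drawn for in-clinic testing "is below the acceptable limits of blood donation of approximately 475 mL per 8 weeks", and concludes from this that the draws add no unacceptable risk.

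The volume estimate is in Protocol 4.3.15: "Approximately 43-51 blood samples will be obtained throughout the course of each of the respective visits", and "The estimated amount of blood for each accuracy visit is approximately 2 ml per sample, exclusive of lab draws". Section 4.3.9.3 explains the 2 mL as a 0.5 mL sample after 1.5 mL of waste.

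The sampling rule is in Protocol 4.3.9.2. Sampling is every 15 minutes between 70 and 300 mg/dL and every 5 minutes at ≤70 or ≥300 mg/dL; above 400 mg/dL it may revert to 15 minutes. After a challenge the wording is permissive: "Blood sampling can also be reduced to every 15 minutes after the challenge is met". Further draws are allowed for safety or to recheck a doubtful value, with no number attached. In the visit tables of section 4.3, a challenge may be stopped once 13 (hypoglycemia) or 16 (hyperglycemia) values have been collected, but need not be.

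The visit windows are in Protocol 3.3.3 and, as day ranges, in SAP 4.3. Visit 3 is on Day 1, Visit 4 on Day 6-8 or 13-15, Visit 5 on Day 21-23, Visit 6 on Day 27-37 and Visit 7 on Day 53-67.

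**The concern.** Sections 6 and 8.5 make a statement about every subject and every 8-week period. Section 4.3.15 gives an estimate for a visit in which one challenge is met and sampling then slows. The sampling rule is driven by glucose, so it sets no maximum per visit, and the visit windows can bring five long sampling visits into one 8-week period. An absolute limit follows from an estimate only if the margin is wide or someone keeps count.

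At stake is a safety assurance given in the risk assessment. The protocol lists anemia from blood sampling among the study risks in section 8.5, so the assurance should be one that the procedures actually deliver.

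**Working it through.** **Inputs.** Limit 475 mL in 56 days (sections 6 and 8.5). Volume 2 mL per sample (4.3.15). Sampling for 8 hours at Visits 3-10 and 10 hours at Visit 11 (4.3). HbA1c draw of about 2 mL at screening (4.1). Visit windows as given above.

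**1. Reproducing the plan's own figures.** Samples per visit = 1 + (minutes at 15-minute spacing)/15 + (minutes at 5-minute spacing)/5.

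- 8 hours, no challenge: 1 + 480/15 = 33.
- 8 hours, hypoglycemia challenge of 60 minutes: 1 + 420/15 + 60/5 = 41.
- 8 hours, hyperglycemia challenge of 75 minutes: 1 + 405/15 + 75/5 = 43.
- 10 hours, hyperglycemia challenge of 75 minutes: 1 + 525/15 + 75/5 = 51.

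So the 43 in section 4.3.15 is the 8-hour figure and the 51 is the 10-hour Day 180 figure. The schedule table in section 4 agrees: 51 × 2 + 2 = 104 mL. The paired-point table in section 11.1.4 implies a planning average of 6720/160 = 42 samples for an 8-hour visit, midway between 41 and 43.

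**2. Visits in any 56 days.** On nominal days at most four accuracy visits fall in 56 days, because Day 1 to Day 60 is too long. With the windows the maximum is five: Day 1, Day 7 or 14, Day 22, Day 30 and Visit 7 on Day 53-56. This holds in either Visit 4 group. Those four days are part of the 15-day Visit 7 window (Day 53-67), so such a subject has no deviation.

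**3. Volume = visits × samples × 2 mL.**

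| Visits in 56 days | Samples per visit | Volume (mL) | Margin to 475 (mL) |
|---|---|---|---|
| 4 (nominal days) | 43 | 344 | 131 |
| 5 | 42 | 420 | 55 |
| 5 | 43 | 430 | 45 |
| 5, plus screening HbA1c | 43 | 432 | 43 |
| 5 | 47 | 470 | 5 |
| 5 | 48 | 480 | −5 |

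The HbA1c row applies only if screening falls in the same 56 days. With Visit 7 on Day 53 that means screening no more than two days before insertion, whereas section 4.1 allows 45.

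**4. What uses up the margin.** Break-even is 475/(5 × 2) = 47.5 samples per visit. The margin of 43-55 mL is 43/2 = 21.5 to 55/2 = 27.5 samples over all five visits. Each 15 minutes at 5-minute spacing in place of 15-minute spacing adds two samples. From 43 samples, 30 more minutes per visit gives 47 samples (470 mL), and 45 more minutes gives 49 samples (490 mL). Equivalently, three extra hours of 5-minute sampling spread over the 5 × 8 = 40 hours adds 24 samples: 430 + 48 = 478 mL.

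**5. The other end of the schedule.** Visit 9 on Day 127, Visit 10 and Visit 11 on Day 177 total 2 × 43 × 2 + 104 = 276 mL. The tight period is the first eight weeks only.

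**The case against.** The strongest reply is that nothing in the plan is miscalculated. Its sample counts and the 104 mL figure reproduce, and even the densest schedule stays under the limit at planned counts. A breach needs two things together: Visit 7 in the first four days of its window, and an average of at least 48 samples, when 43 is already the higher of the two planned challenge counts. From a hypoglycemia visit (41) it takes seven extra samples per visit. A subject in free-range control who stays in range needs only 33. Missed samples and visits stopped for loss of IV access lower the total further. All of this stands, and it limits the point to a thin margin.

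Section 6 can also be read as an instruction to sites, with the optional reductions in 4.3.9.2 used to stay within it. That reading is fair, but 4.3.9.2 is not made subject to the limit, and a site can obey a cumulative limit only if it keeps the cumulative figure. Section 8.5 is in any case worded as a fact. The hematocrit check at each accuracy visit (4.3.3) is a partial safeguard, but it does not measure volume drawn.

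Finally, a running total may exist in visit worksheets, the Monitoring Plan or the Safety Management Plan, none of which is available here, and the blood-volume row of the schedule table is only partly legible. That caveat stands: the statement is confined to the text at hand.

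**Conclusion.** The limit is met on planned figures but is not guaranteed by the procedures. A subject who is within every window and sampled according to 4.3.9.2 can pass 475 mL if five visits fall in 56 days and average 48 samples or more; the margin before that is about 43-55 mL. This is a cheap improvement to a safety statement, not an error in the plan's arithmetic.

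The result assumes, as 4.3.15 does, that the 1.5 mL waste is lost. The protocol describes no return of it; if it were returned, five visits of 43 samples would draw 5 × 43 × 0.5 = 107.5 mL and the issue would disappear. Fingersticks and any venous hematocrit draw are not counted and would narrow the margin.

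Three stronger readings are tempting and not supported:

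- A reader might multiply the upper figure of 51 by five visits and obtain 510 mL, or 512 mL with an HbA1c draw. As a planned count, 51 belongs to the 10-hour Day 180 visit. Reaching it in an 8-hour visit takes 60 minutes more of 5-minute sampling than the planned 75, and no document figure supports that at all five visits.
- A reader might conclude that the Visit 7 window has to change. It does not; a count or a restated claim resolves the matter with the window as it is.
- A reader might infer that blood loss will cause missed visits through the hematocrit condition. The documents give no figure from which to judge that.

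**What to change.** Reconcile Protocol sections 4.3.9.2, 4.3.15, 6 and 8.5 in one of two ways:

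- Keep the limit as a commitment. Record a running 8-week blood volume for each subject on the visit worksheet, including waste and laboratory draws, and check it against the protocol's own limit before and during sampling. Section 4.3.9.2 should then refer to that check.
- Or restate sections 6 and 8.5 as an expected volume, and show the five-visit case (about 420 mL at 42 samples, 430-432 mL at 43) beside the nominal 344 mL.

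If a cumulative record already exists in another study document, a cross-reference in section 6 is enough. How sampling is adapted when a subject nears the limit is for the sponsor and investigators to decide.

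The cost is one worksheet field or a few sentences of protocol text, and under the first option possibly a few optional samples.
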